## 6.0 STUDY OBJECTIVES AND ENDPOINTS

Objectives	Endpoints
Primary	

 
To assess the feasibility of MFE-HD-tDCS plus simultaneous computerized CT as a viable intervention to improve cognitive function in patients with MCI.
 
	
 
Treatment completion rates (Primary)
 
Consent rates.
 

Secondary	

 
To collect preliminary data on the efficacy of MFE-HD-tDCS with simultaneous computerized CT, administered in 15 sessions over a period of 3 months, to improve cognition in subjects with MCI.
 
To collect preliminary data on the efficacy of MFE-HD-tDCS in combination with computerized CT, administered in 15 sessions over a
 
	
 
ADCS PACC score at 3 and 6 months.
 

[figure not shown]
period of 3 months to improve quality of life in subjects with MCI.	

 
To collect preliminary data on the effects of MFE-HD-tDCS combined with computerized CT on brain function and on neurodegeneration.
 
	
 
Neurite density (intracellular volume fraction) at 3 months
 
Diffusivity indices: Fractional anisotropy(FA), Mean(MD), Axial(AD), Radial(RD) Diffusivity at 3 months
 
Morphometric indices: Cortical thickness, Surface Area, Volume, gyration index at 3 months
 
ASL perfusion indices: blood flow, blood volume, mean transit time, time to peak, at 3 months
 

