#### Brief Description of Study Groups

20 participants with MCI, ages 50-90 years, will be assigned to one of two groups:

1. Active HD-tDCS + cognitive training (n=10)
2. Sham-HD-tDCS + cognitive training (n=10)

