## **9.4 Study Intervention Compliance**

Threshold adherence/compliance is achieved when the enrolled participant completes all HD-tDCS/sham HD-tDCS + CT sessions and undergoes cognitive testing at 0, 3 and 6 mo. This degree of participation will allow calculation of the primary outcome, i.e. treatment completion rates.

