## 12.2 Sample Size Justification

Given the pilot nature of this study, two feasibility outcomes will be included: Consent rate and treatment completion rate. 20 patients are enough to calculate a 90% exact binomial confidence interval of (.75, 1) if all 20 are observed to complete treatment. Thus, this sample size is large enough to potentially exclude completion rates of 3/4 or lower. The pilot data from this study will provide initial estimates of the variability and the effect sizes; This information will then be used for the formal calculations of power and sample size necessary to conduct a future phase II trial.

This pilot study, if successful, would prove the feasibility of the proposed approach. Treatment completion rates of less than 75% could be reasonably excluded if all 20 patients are observed to complete treatment. Additionally, recruiting and consenting 20 patients over a period of 3 months would support the feasibility of conducting a larger-scale, 2-site, phase II trial with 120 MCI patients over a span of 5 years (i.e. approximately 32 patients/year). This would be the necessary next step in the path to using combined HD-tDCS/CCT as an intervention that could lead to tangible clinical improvements. This future trial would use a 2 X 2 factorial design that would allow for the inclusion of a 'true' control group (i.e. sham HD-tDCS/sham CCT). The stimulation period would be extended (six months instead of three) with the hope of inducing longer lasting effects that could translate into a slowing of disease progression; Accordingly, we would evaluate the effects of the intervention at 6, 12 and 18 months. MRI changes would be assessed at 12 months, as well as the effect on cerebrospinal fluid (CSF) AD biomarkers of a subset of patients. **Sample size justification for future phase II trial (N=120)**. Driven by the efficacy outcome of change in ADCS-PACC score from baseline to 12 months. We presume that 10% of these patients are lost to follow up before one year. We further presume that the main aim will be addressed by a two-sided test at the .05 level of the hypothesis that the improvement rate in the true HD-tDCS group exceeds that of the sham group. Under these assumptions there is a minimum 90% power to detect a 31% difference in improvement rates. Thus, this design has good power to find a moderate effect size of HD-tDCS treatment.

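### The completion rate and its 75% statement pool active and sham subjects, and no active-arm estimate is planned, so the precision for the intervention itself goes unstated

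*Combined protocol and SAP*

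**What the plan says.** Section 6.0 gives the primary objective as "To assess the feasibility of MFE-HD-tDCS plus simultaneous computerized CT as a viable intervention to improve cognitive function in patients with MCI". The primary endpoint beside it is the treatment completion rate, with no arm named.

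Section 9.4 supplies the definition. A subject meets the threshold who "completes all HD-tDCS/sham HD-tDCS + CT sessions and undergoes cognitive testing at 0, 3 and 6 mo", and the section says this participation is what allows the primary outcome to be calculated. Active and sham subjects therefore count alike.

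Section 7.1 assigns 10 subjects to active stimulation and 10 to sham, all with active cognitive training. The precision statement in section 12.2, repeated in the synopsis (3.1), uses the whole sample: "20 patients are enough to calculate a 90% exact binomial confidence interval of (.75, 1) if all 20 are observed to complete treatment". It continues: "Thus, this sample size is large enough to potentially exclude completion rates of 3/4 or lower". Section 12.2 then restates the conclusion, again for the whole sample: "Treatment completion rates of less than 75% could be reasonably excluded if all 20 patients are observed to complete treatment".

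No section plans a completion estimate, interval or threshold by arm. Sections 12.3 and 12.4 are written mainly for a future phase II trial and do not fill the gap.

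**The concern.** The objective asks whether people with MCI can complete the active combination. The estimate planned to answer it is half comparator.

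Under section 9.1, the arms share visits, cap, gel and training but differ in exposure to current. Active subjects receive 20 minutes per network, 80 minutes per session, for 15 sessions. Sham current is ramped down after 30 seconds on each network. Sham completers therefore inform the burden of the procedures, but not the tolerability of sustained current.

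The sponsor's preparatory study (section 5.4) involved five healthy adults, so completion under active current in MCI is something this pilot has to show. Section 12.2 says a successful pilot would establish feasibility and lead to a 120-patient trial with stimulation extended from three to six months. A reader planning that trial needs the active-arm completion rate and its uncertainty, and the plan states neither.

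**Working it through.** **Inputs.** Pooled n = 20, confidence 90%, exact binomial method, benchmark 75% (12.2); 10 active and 10 sham (7.1); anticipated dropout about 10% (3.1). Sidedness is not given. I take two-sided, the usual meaning of a 90% interval, and show one-sided beside it.

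**Formula.** When all n subjects complete, the exact (Clopper-Pearson) lower limit is (α/2)^(1/n) two-sided or α^(1/n) one-sided, with α = .10. With fewer completers the limits are beta quantiles.

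**The plan's own figure.** For 20/20:
- Two-sided: .05^(1/20) = .861, so the interval is (.861, 1), not (.75, 1).
- One-sided: .10^(1/20) = .891.
- A lower limit of .75 at n = 20 corresponds to two-sided confidence of 1 − 2 × .75^20 = .994.
- P(20/20 | p = .75) = .75^20 = .003.

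The printed limit does not reproduce, but the conclusion that 20/20 excludes 75% is true with room to spare. That numerical slip is a separate matter: correcting it makes the pooled statement look stronger and still says nothing about the active arm.

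**Active arm alone, two-sided 90% exact intervals.**
- 10/10: .05^(1/10) = .741, giving (.741, 1). This misses .75 by .009. Equivalently, P(10/10 | p = .75) = .75^10 = .056, just above .05.
- 9/10: (.606, .995).

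**Active arm alone, one-sided 90%.**
- 10/10: .10^(1/10) = .794, which excludes 75%.
- 9/10: P(at least 9/10 | p = .75) = .75^10 + 10 × .25 × .75^9 = .056 + .188 = .244. This exceeds .10, so 75% is not excluded.

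**How much the pooled rate could mask.**
- 20/20 requires active 10/10. Nothing is masked.
- 19/20: pooled two-sided lower limit .784, above .75. One active dropout (9/10) could sit behind this.
- 18/20: pooled two-sided interval (.717, .982), which no longer excludes 75%. This is also the result implied by the anticipated 10% dropout. Read one-sided, its lower bound is .755, which just clears 75%.

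**Illustration, on assumed rates.** If true active completion were .75 and every sham subject completed, the chance of at least 19/20 pooled would be the .244 computed above. The chance of 20/20 would be .056.

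**The case against.** The strongest reply is that section 12.2 makes its claim at one result only, 20/20, and that result requires every active subject to complete. A reader might infer that feasibility could be declared while active completion is poor, with sham completers filling the numerator. The documents do not support that. At 20/20 nothing is hidden. At 19/20, where the plan makes no claim, an active result of 9/10 is the worst possible, and an observed 90% is imprecise rather than poor. This part of the objection stands.

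A reader might also infer that the wrong group is counted and that sham completers are uninformative. That goes too far. Both arms attend 15 visits of about 2.5 to 3 hours (10.2), wear the cap and do 60 minutes of active training. Training is half of the combined intervention, and the envisaged phase II trial would itself use sham controls. Overall completion is a legitimate measure of whether such a trial can be run.

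Nor do the documents show that active subjects will drop out more often. All five healthy adults in the preparatory study completed, and the events reported there (tingling, redness, a sensation lasting three hours, a headache that resolved) are not linked to dropout. Section 8.6 lists adverse events as a possible reason for withdrawal, which makes a difference between arms plausible but not demonstrated.

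Finally, the plan contains no go/no-go rule. It also cites recruiting and consenting 20 patients in three months as evidence of feasibility. To say that the phase II decision rests on the completion rate alone would be inference.

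What survives is narrower: the objective names the active combination, the only planned estimate and precision statement are pooled, and nothing by arm is specified. The plan does not forbid reporting by arm, but it does not provide for it.

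**Conclusion.** The point holds, at moderate severity. The 75% exclusion describes completion of trial procedures across both arms and should not be read as the precision for active stimulation with training.

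The best possible active result leaves a two-sided lower limit of about .74 instead of the .861 available from the pool; a single active dropout brings it to .606. The 10/10 shortfall against 75% is under one percentage point and depends on the two-sided reading, so it would be wrong to say flatly that 10/10 cannot exclude 75%. The mismatch between objective and estimate does not depend on sidedness, and at 9/10 the active arm fails to exclude 75% on either reading.

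These figures assume 10 treated subjects per arm and the exact binomial method that the plan names.

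**What to change.** - **Sections 6.0 and 9.4:** keep the pooled completion rate, described as a measure of trial-procedure feasibility. Add completion by arm with exact 90% intervals, and name active-arm completion as the estimate that addresses feasibility of the intervention.
- **Section 12.2, and its repeat in 3.1:** state whether the 90% interval is one- or two-sided. Say that the 75% exclusion applies to the pooled rate, and that the active arm alone (n = 10) gives at best a lower limit of about .74 two-sided (.794 if a one-sided bound is chosen). Correct the 20/20 interval in the same edit.

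Making the active arm the sole primary estimate is not required. On the two-sided reading no result in 10 subjects could then meet the 75% benchmark, and that trade-off is for the sponsor to weigh.

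The cost is wording and a table row or two, with no extra patients or data. The downside is that the stated precision for the intervention becomes less favourable than the pooled figure.

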## 12.3 Subject Population(s) for Analysis

In a future phase II trial, all analyses will be done under the intent-to-treat principle as far as allowed by patient consent and follow-up. All consenting patients will be followed even if they are noncompliant. Potentially confounding patterns of loss to follow-up will be investigated via sensitivity analyses [Panel on Handling Missing Data in Clinical Trials, Committee on National Statistics Division of Behavioral and Social Sciences and Education US National Research Council. The Prevention and Treatment of Missing Data in Clinical Trials. National Academies Press, 2010].

## 12.4 Statistical Methods

**In a future phase II trial** (and for this feasibility trial as appropriate), baseline clinical and demographic characteristics will be tabulated for subjects assigned to the four treatment modes in a future 2 X 2 factorial design. Comparison of these characteristics between the four groups will be carried out with t-tests and chi-square tests. If important differences are found between the groups at baseline, the statistical analyses will be repeated after adjusting for these differences. These analyses will be considered to be supportive however.

All analyses will be done under the intent-to-treat principle as far as allowed by patient consent and follow up. All consenting patients will be followed even if noncompliant. Potentially confounding patterns of loss to follow up will be investigated via sensitivity analyses.

The primary outcome variable is efficacy, defined as improvement over time in ADCS-PACC scores from baseline to 12 mo. This will be analyzed via a standard 2 x 2 x 2 analysis of covariance, where the three two-level factors are the two treatments and MCW vs. UW-Madison site, and the continuous covariate is the value of the outcome at baseline. Explicitly,

$$\mu_i = \beta_0 + \beta_{HD-tDCS} \times I(HD-tDCS_i) + \beta_{train} \times I(train_i) + \beta_{inter} \times I(HD-tDCS_i) \times I(train_i) + \beta_{base} \times Y_{i,base},$$

where:  $\mu_i$  is the mean outcome, indexed by  $i$  for subject;  $\beta_0$  is the intercept term,  $\beta_{\text{HD-tDCS}}$  is the HD-tDCS main effect term,  $I(\text{HD-tDCS}_i)$  is an indicator variable for the  $i$ th patient taking the value of 1 if s/he received true HD-tDCS and 0 for sham;  $\beta_{\text{train}}$  is the cognitive training main effect term;  $I(\text{train}_i)$  is an indicator variable for true vs. sham cognitive training in the  $i$ th patient;  $\beta_{\text{inter}}$  is the interaction term between the two treatments, measuring their synergy;  $\beta_{\text{base}}$  is the coefficient for baseline outcome level; and  $Y_{i,\text{base}}$  is the baseline outcome level for patient  $i$ . For the primary aim the outcome would be cognitive function measured by ADCS-PACC score at 12 mo (since baseline ADCS-PACC score is included, this is formally equivalent to change in 12-mo ADCS-PACC score from baseline).

All hypotheses in the primary and secondary aims could be examined by testing appropriate parameters using the relevant endpoints in the above model. The primary aim of examining overall 12-mo HD-tDCS will be effected by estimating  $\beta_{\text{HD-tDCS}}$  and  $\beta_{\text{inter}}$ , accompanied by confidence intervals and a 2-degree-of-freedom test that they are both 0. Rejection of such a test is evidence that HD-tDCS does affect patient's 12-month cognition. Similarly, therapy's effectiveness can be examined in this population by estimating  $\beta_{\text{train}}$ . The interaction parameter  $\beta_{\text{inter}}$  measures the two treatments' synergy, the degree to which CT potentiates the effects of HD-tDCS. Since all study outcomes are continuous, models will be fit using ordinary least squares.

The full 18 mo longitudinal trajectory will be modeled using a repeated measures Laird-Ware formulation (Fitzmaurice, GM, Laird, NM, and Ware, J. *Applied Longitudinal Analysis, 2nd Edition*. Wiley; New York, NY. 2011), equivalent to that stated above but with intra-subject error terms added and average changes modeled instead of single 12 mo values as fixed effects.

**Analysis of cognitive data:** To analyze the effect of training on outcome measures, a 2 x 4 mixed-factor analysis of variance (ANOVA) will be employed, including a within-subject factor of test performance over time (pre- vs. post-training) and a between-subjects factor of group assignment. We will use Bonferroni correction to conservatively control for familywise error. If analyses reveal that the groups were not equivalent at baseline, we will employ statistical covariates in order to control for group differences.

We will utilize adherence data to determine how many participants follow the training schedule. Threshold adherence is achieved when the enrolled participant completes all HD-tDCS/sham HD-tDCS + CT/sham-CT sessions and undergoes cognitive testing at 12 mo. This degree of participation will allow calculation of the primary outcome, i.e. change in ADCS-PACC at 12 mo. We will exclude data from participants who did not meet the minimum threshold of adherence to the interventions.

Finally, if statistically significant improvements in neuropsychological outcome measures are shown, will conduct follow-up analyses using reliable change index (RCI) scores. The RCI allows for an assessment of the magnitude of change of scores for an individual that are not susceptible to group means and standard deviations. This process has been described in detail elsewhere (Hinton-Bayre, 2010; Maassen et al., 2009). We will use the Jacobson-Truax method with a 0.90 confidence interval, which indicates a 95% chance of true improvement for anyone who passes the threshold (Jacobson & Truax, 1991).

**Neuroimaging:** In a future larger-scale phase II trial We will perform Kruskal-Wallis tests, to determine if there are significant between group differences at 12 mo, on each of the NODDI (neurite orientation dispersion (OD) index, neurite density (or intracellular volume fraction) (Vic,), and diffusivity (FA, MD, RD) measures, as well as measures of neurodegeneration measured by cortical thickness and ASL perfusion (cerebral blood volume, mean transit time, time to peak etc). Post-hoc analyses comparing the sham group to each of the three remaining groups will be done

**using Mann-Whitney U tests. All analyses will be done with and without controlling for possible confounding factors such as age, intracranial volume, family history of AD or other dementias.**

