	
 
• Consent rate
 
• ADCS PACC score at 3 and 6 months
 
• Neurite density (intracellular volume fraction) at 3 months
 
• Diffusivity indices: Fractional anisotropy (FA), Mean (MD), Axial (AD), Radial (RD)
 
• Diffusivity at 3 months
 
• Morphometric indices: Cortical thickness, Surface Area, Volume, gyration index at 3 months.
 
• ASL perfusion indices: blood flow, blood volume, mean transit time, time to peak, at 3 months
 

Study Design	The study design is a double-blinded, randomized pilot clinical trial of HD-tDCS/sham HD-tDCS combined with CT, administered to subjects with amnestic MCI (aMCI) in blocks of 5 daily treatments for a total of 15 sessions. There will be one treatment block/month for a total of 3 months. 20 participants with aMCI will be enrolled. There will be 2 treatment groups/arms with 10 subjects per group/arm. We anticipate a dropout rate of appr. 10% and aim to complete procedures in 20 subjects.
Study Intervention	High definition transcranial direct current stimulation (HD-tDCS) Sham HD-tDCS Computerized Cognitive training (CCT) Sham CT
Total Number of Subjects	20
Study Population	Male and females aged 50 to 90 years with established diagnosis of MCI amnestic type. Total of 20 subjects
Statistical Methodology	Given the pilot nature of this study, two feasibility outcomes will be included: Consent rate and treatment completion rate. 20 patients are enough to calculate a 90% exact binomial confidence interval of (.75, 1) if all 20 are observed to complete treatment. Thus, this sample size is large enough to potentially exclude completion rates of 3/4 or lower. The pilot data from this study will provide initial estimates of the variability and the effect sizes. This information will then be used for the formal calculations of power and sample size necessary to conduct a future phase II trial.
Estimated Subject Duration	The duration of the study for each subject is approximately 6 months.
Estimated Enrollment Period & Study Duration	Study enrollment and follow-up will occur over 9 months with the total expected duration of the trial to be 12 months.

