### Baseline Visit

Prior to any procedures, informed consent will be obtained. Visit procedures may take up to 7 hours but may be more or less depending on time needed for breaks, participant comfort, and scanner set-up. This baseline visit will likely be completed over 2-3 days but can be completed over multiple days prior to Visit 2.

Once consent is obtained, the following assessments will be completed, and information collected for study participants.

- Document informed consent
- Review eligibility based on inclusion/exclusion criteria
- Demographics (age, sex, race, ethnicity, age, year of birth)
- Medical history
- Physical and Neuro exam including vitals
- Medications
- Cognitive battery
- Structural MRI
- TMS Neuro-navigation (MCW only)
- Study Partner Questionnaires

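### Section 12.4 gives two cognitive analyses that disagree on baseline adjustment (one always adjusts, one only if groups look unequal) and assigns neither to the pilot's 3- and 6-month outcomes

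*Combined protocol and SAP*

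**What the plan says.** The synopsis (3.1) sets the size of the pilot: "There will be 2 treatment groups/arms with 10 subjects per group/arm". Cognition is assessed at baseline, month 3 and month 6, and ADCS-PACC at 3 and 6 months is a secondary endpoint (sections 6.0 and 12.1).

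Section 12.4 opens by saying that it describes a future phase II trial and applies to this feasibility trial where appropriate. It then contains three statements on baseline adjustment:

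- **Baseline characteristics.** "Comparison of these characteristics between the four groups will be carried out with t-tests and chi-square tests". Then: "If important differences are found between the groups at baseline, the statistical analyses will be repeated after adjusting for these differences". These repeated analyses are labelled supportive.
- **ADCS-PACC model.** An ANCOVA of the 12-month score on the two treatment factors, site and the baseline score. The baseline score enters unconditionally. The text adds that the primary and secondary hypotheses could be examined in this model.
- **Analysis of cognitive data.** "a 2 x 4 mixed-factor analysis of variance (ANOVA) will be employed", with time (pre versus post) as the within-subject factor and group as the between-subject factor. Here: "If analyses reveal that the groups were not equivalent at baseline, we will employ statistical covariates in order to control for group differences". No covariate, test, significance level or equivalence margin is named, and the adjusted result is not called supportive.

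**The concern.** The two models handle baseline differently, and nothing says which one produces the pilot's cognitive results. Neither fits the pilot as written. The ANCOVA has a 12-month outcome and a factorial of two treatments; the mixed ANOVA has four groups and two time points. The pilot has two arms and three assessments. An analyst could choose either model after seeing the data.

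The conditional rule is also the weaker of the two. Under randomisation any baseline difference is due to chance, so a test of that difference examines a null already known to be true. A non-significant result with 10 per arm does not show that the groups are alike. The final model then depends on the observed baseline data, and moderate imbalances are left unadjusted.

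At stake are the estimates of effect size and variability that section 12.2 says will be used for the phase II power and sample size calculations.

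**Working it through.** The plan gives no figure for the baseline comparison, so there is none to reproduce.

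**Inputs from the documents**
- 10 per arm (3.1), or 9 per arm after about 10% dropout (10 × 0.9).
- Phase II: 120 patients in four groups, so 30 per group, or 27 after 10% loss (12.2, 12.4).
- t-tests for baseline characteristics (12.4).

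**Assumptions**
- A two-sided 0.05 level for the baseline test. The plan states "a two-sided test at the .05 level" only for the phase II main hypothesis (12.2), so other levels are shown.
- Correlation rho between baseline and follow-up of 0.5 to 0.9, with equal SDs at both times. The documents give no value.
- In a flagged trial, the covariate added is the baseline score. The plan does not name it.

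**Step 1: the imbalance that goes unflagged.** The smallest observed difference that reaches significance, in SD units, is t(1 - alpha/2, 2n - 2) × sqrt(2/n).

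| n per arm | alpha | cut-off |
|---|---|---|
| 10 | 0.05 | 2.101 × 0.447 = 0.94 SD |
| 9 | 0.05 | 1.00 SD |
| 10 | 0.10 | 0.78 SD |
| 10 | 0.20 | 0.60 SD |
| 30 (phase II) | 0.05 | 0.52 SD |
| 27 (phase II) | 0.05 | 0.55 SD |

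**Step 2: how often this matters.** The chance imbalance in one covariate has standard error sqrt(2/10) = 0.447 SD. So P(|imbalance| > 0.5 SD) = 2 × (1 - Phi(0.5/0.447)) = 0.26. The test flags 5% of trials, nearly all of them with imbalances above 0.5 SD. That leaves about 0.26 - 0.05 = 0.21 with an imbalance above 0.5 SD and no flag; simulation agrees.

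**Step 3: what remains in the pre/post contrast.** With two groups and two times, the time-by-group contrast is the difference in mean change, dY - dX. Given the baseline imbalance dX, the expected value of dY is the true effect plus rho × dX. The contrast is therefore off by (rho - 1) × dX. The simulated slopes of the estimate on dX in unflagged trials (200,000 trials per setting) were -0.499, -0.300, -0.203 and -0.099 at rho 0.5, 0.7, 0.8 and 0.9, against 0.00 for ANCOVA.

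In unflagged trials with the active arm more than 0.5 SD ahead, the mean imbalance is about 0.66 SD. The average error is then:
- rho 0.5: -0.5 × 0.66 = -0.33 SD
- rho 0.7: -0.3 × 0.66 = -0.20 SD
- rho 0.8: -0.2 × 0.66 = -0.13 SD
- rho 0.9: -0.1 × 0.66 = -0.07 SD

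The sign reverses when sham is ahead, so the average over all randomisations is zero.

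**Step 4: precision and power.** The conditional rule (change score unless baseline p < 0.05) was compared with ANCOVA on the baseline score alone, 10 per arm. Power is for an assumed true effect of 0.8 SD.

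| rho | SD of estimate, conditional | SD of estimate, ANCOVA | power, conditional | power, ANCOVA |
|---|---|---|---|---|
| 0.5 | 0.435 | 0.399 | 39% | 47% |
| 0.7 | 0.342 | 0.329 | 59% | 63% |
| 0.8 | 0.282 | 0.276 | 76% | 78% |
| 0.9 | 0.201 | 0.202 | equal | equal |

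**The case against.** The strongest reply is that the plan already contains the remedy: the ADCS-PACC ANCOVA includes the baseline score whatever the baseline comparison shows. That stands. A reader might infer from the conditional sentence that covariates enter any cognitive analysis only after a failed baseline test; the documents do not support this. The conditional rule belongs to the mixed ANOVA. But the ANCOVA is written for 12 months and four groups, and the text says only that hypotheses could be examined in it, so the pilot's model is still unassigned.

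Other replies also stand in part:

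- The rule sits in a four-group analysis meant for phase II. Ten per arm, and so the 0.94 SD cut-off, applies only if the rule is carried over to the pilot. No other cognitive analysis is given for the pilot, and at phase II size the cut-off is still about 0.52 to 0.55 SD.
- A reader might infer that the rule for clinical and demographic characteristics also switches the main model. It does not: those adjusted analyses are repeats, labelled supportive, and they are triggered by important differences rather than a stated significance level.
- A reader might infer that the whole imbalance stays in the estimate, or that the estimator is biased. Because the pre-score is part of the ANOVA response, only a fraction (1 - rho) remains, with opposite sign, and the average error is zero. Under the assumed test, the largest imbalances are the ones adjusted.
- A reader might go further and call for age, premorbid ability (WRAT-4) or education as covariates. The documents do not show that these predict outcome beyond the baseline score. If two added covariates do not, simulated power at 0.8 SD falls to about 42%, 57% and 72% at rho 0.5, 0.7 and 0.8. That is below the conditional rule at 0.7 and 0.8.

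**Conclusion.** The point holds in this form: section 12.4 leaves the pilot's cognitive analysis undecided between an unconditional ANCOVA and a mixed ANOVA with a data-dependent covariate rule, and the second is the poorer choice. The wording should be corrected; the trial's main conclusion is not at risk.

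The harm is conditional. It affects about one randomisation in five and depends on rho: material at 0.5, small at 0.9. Averaged over randomisations, the loss of precision is modest at rho 0.5 (SD of the estimate 0.435 against 0.399), slight at 0.8, and absent at 0.9. These sizes rest on the assumed 0.05 t-test, the assumed range of rho, and use of the rule with 10 per arm. The inconsistency between the two models rests on none of these. Treatment completion rate, the primary endpoint, is not touched.

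**What to change.** In section 12.4:

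1. State that, in this pilot, ADCS-PACC and each other cognitive outcome at 3 and 6 months are analysed by ANCOVA with treatment arm, that outcome's own baseline value and site, whatever the baseline comparison shows. This is the existing ANCOVA reduced to two arms. Site is listed as a factor in the text but has no term in the displayed equation, so write it in.
2. Delete the sentence in the cognitive-data paragraph that makes covariates depend on non-equivalence at baseline.
3. Tabulate baseline characteristics by arm descriptively, without t-tests or chi-square tests.

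The baseline scores are already collected, so the change is wording only. The statistical cost is one error degree of freedom for the baseline score and one for site: 18 falls to 16, and the 0.05 critical t rises from 2.101 to 2.120.
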